# Secondary Endpoints Assessing Cardiac Valve Function and Pulmonary Arterial Pressure: (revised per Amendment 02)

- Proportion of subjects without FDA-defined valvulopathy at Baseline who develop FDA-defined valvulopathy at 1 year (see Section 8.4 for definition)
- Proportion of subjects with FDA-defined valvulopathy confirmed by documented objective assessments at Baseline who demonstrate worsened FDA-defined valvulopathy (see Section 8.4.1 for definition) at 1 year (revised per Amendment 01).
- Change from Baseline in estimated pulmonary artery systolic pressure at 1 year

## **5.1.4** Exploratory Endpoints

- Change from Baseline in CV risk factors at 1 year and yearly thereafter (e.g., body weight, dyslipidemia, insulin level, hypertension, and applicable biomarkers of CV risk and other end-organ diseases). For lipid parameters percent change from baseline will be used
- Change from Baseline in eGFR and ACR at 1 year, yearly thereafter, and at the end of the study. GFR will be estimated using creatinine, cystatin C and a combination of both (Section 8.1).
- Change from Baseline in LFTs (AST, ALT, alkaline phosphatase, GGT, total and direct bilirubin) at 1 year and yearly thereafter
- Proportion of subjects without FDA-defined valvulopathy at Baseline who develop FDA- defined valvulopathy at 2 years and yearly thereafter
- Change from Baseline in estimated pulmonary artery systolic pressure at 2 years and yearly thereafter
- Proportions of subjects with at least a 1-stage reduction in an obesity-related complication (prediabetes, metabolic syndrome, T2DM, hypertension, and hypertriglyceridemia/dyslipidemia) at 1 year and EOS; incidence of other obesity-related complications will be collected through AE reports, medical history, and use of

concomitant medications, based on 2014 Advanced Framework for a New Diagnosis of Obesity as a Chronic Disease (American Association of Clinical Endocrinologists [AACE] and American College of Endocrinology [ACE]). (revised per Amendment 01)

- Change from Baseline in HbA1c, FPG, fasting insulin levels, and homeostatic model assessment insulin resistance (HOMA-IR) at 6 months in the following subpopulations of subjects with T2DM at Baseline: (revised per Amendments 01 and 02)
  - o Subjects with (HbA1c>7%) at Baseline
  - o Subjects who have not been treated with antidiabetic agents at Baseline
  - o Subjects who are on monotherapy with oral antidiabetic agent at Baseline
  - Subjects with early T2DM (duration of diagnosis of diabetes is less than 5 years)
     at Baseline
- Proportion of subjects with reduction in the number of OAD medications or reduction in the dosage of OAD medications at 6 months in the following subpopulations of subjects with T2DM at Baseline: (revised per Amendment 01)
  - o Subjects with (HbA1c > 7%) at Baseline
  - o Subjects who are on monotherapy with oral antidiabetic agent at Baseline
  - Subjects with early T2DM (duration of diagnosis of diabetes is less than 5 years) at Baseline
- Proportions of subjects with prediabetes at Baseline who develop new diagnosis of diabetic retinopathy or new diagnosis of diabetic neuropathy by EOS (revised per Amendment 01)
- Proportions of subjects with T2DM at Baseline who develop new diagnosis of diabetic retinopathy or new diagnosis of diabetic neuropathy by EOS (revised per Amendment 01)

## 5.2 STUDY SUBJECTS

#### **5.2.1** Definitions of Analysis Sets

The number (percent) of subjects included in each analysis set will be presented by analysis set, treatment group and overall. The description of the analysis data sets are:

- The Safety Analysis Set: will be the group of subjects who received at least one dose of study drug and had at least one post dose safety assessment.
- The Intent-to-Treat (ITT) Set: will be the group of all randomized subjects regardless of whether they took study drug or not. This is the same as the Full Analysis Set.
- Total Time Analysis Set: Using the ITT, events are counted that occur while subjects are on and off treatment. Subjects with no events will be censored at their last study contact or at the visit following Sponsor Notification of Study Completion, whichever

- occurs first. This analysis set will be used for the primary analysis. See Section 8.5 for censoring algorithm.
- On-Treatment plus 30 Days Analysis Set: Using the ITT, events are counted that occur
  while subjects are "on treatment" and up to 30 days from their last dose. Subjects with
  no events who discontinue early or complete the study will be censored at their last dose
  date plus 30 days. See Section 8 for definition of "on treatment" and Section 8.5 for
  censoring algorithm.
- On-Treatment Analysis Set: Using the ITT, events are counted that occur while subjects are "on treatment". Subjects with no events who discontinue early or complete the study will be censored at their last dose date. See Section 8 for definition of "on treatment" and Section 8.5 for censoring algorithm.
- Prediabetes Analysis Set: This set includes all subjects in the ITT set without a history of any type of diabetes and who are prediabetic at Baseline (defined in Section 8).
- Nondiabetes Analysis Set: This set includes all subjects in the ITT set without a history of any type of diabetes at Baseline (defined in Section 8).
- T2DM Analysis Set: This set will be all subjects in the ITT who have T2DM at Baseline (defined in Section 8).
- FDA-defined Valvulopathy Analysis Set: This set will be all subjects in the ITT without FDA- defined valvulopathy at Baseline (defined in Section 8.4). The data from the ECHO sub-study will be pooled with the ECHO data from the 3 pivotal lorcaserin HCl studies (APD356-009, APD356-010, and APD356-011).
- The PD Analysis Set will be the group of subjects who have both baseline and at least one post-baseline assessment of at least one PD parameter.

Details of the censoring algorithms for time-to-event endpoints are presented in Section 8.5.

#### 5.2.2 Subject Disposition

The number of subjects screened and the number (percent) of subjects who failed screening and the reasons for screen failure will be summarized, based on data reported on the Screening Disposition CRF. The distribution of the number of randomized subjects enrolled by each site will be summarized for each randomized treatment group. The primary reasons for screen failures; did not meet inclusion/exclusion criteria, AE, lost to follow-up, withdrawal of consent, and other, will be presented.

For study completion, the number (percent) of randomized subjects who completed the study (e.g. subject was in the study at the date of Final Sponsor Notification/Premature Study Discontinuation by Sponsor, whether subject is on or off treatment or death) and who

discontinued from the study will be summarized according to the primary reason for discontinuation based on data reported on the Final Study Disposition CRF. The number (percent) will be presented by treatment group and total for subjects; randomized, not treated, treated, who completed the study, and discontinued from the study. For those who are considered to have discontinued from the study, the reasons for discontinuation from the study at Final Sponsor Notification/ Premature Study Discontinuation are captured in the Final Study Disposition CRF (Withdrawal of Consent, Lost to follow up, Study prematurely terminated by sponsor, and Other).

Completion of Study Treatment: the number (percent) of randomized and treated subjects who completed study treatment (e.g. subject was on study drug at the date of Final Sponsor Notification/Premature Study Discontinuation by Sponsor) and who discontinued from study treatment will be summarized according to the primary reason for discontinuation, based on data reported on both the Final Study Disposition CRF and Early Discontinuation from Study Drug CRF. The number (percent) will be presented by treatment group and total for subjects; randomized, not treated, treated, who completed study on treatment, off treatment, and discontinued from study treatment. The reasons for early discontinuation from study drug are: AE/SAE, Pregnancy/Breastfeeding, Subject choice unrelated to AE/SAE, Treatment Required with Prohibited Concomitant Medications, Other – study administrative reasons. Subject choice will be further summarized as per the reasons captured in the Early Discontinuation from Study Drug CRF; Inadequate Therapeutic Effect, Logistical reason, and Other.

#### 5.2.3 Protocol Deviations

Major protocol deviations will be summarized, number (%), in addition a subject listing will be provided along with the description of the protocol deviation. Protocol deviations will be identified prior to database lock.

#### **5.2.4** Demographic and Other Baseline Characteristics

Demographic and other baseline characteristics will be summarized as outlined for the Safety Analysis Set and ITT in aggregate as well as stratified by CV strata, baseline glycemic status (e.g. normal glucose homeostasis, prediabetes, nondiabetes, and T2DM at baseline as defined in Section 8).

Continuous demographic and baseline variables include age, height, weight, waist and hip circumference, duration of comorbid conditions (none, hypertension, dyslipidemia, sleep apnea, coronary artery disease (CAD)/CV disease), duration of T2DM, HbA1c, and BMI.

Categorical variables include sex, age group (<65 years,  $\geq$ 65 to < 75, ,  $\geq$ 75 years), race, ethnicity, HbA1c (prediabetes: 5.7% to <6.5%; normal glucose homeostasis: <5.7%), BMI (<30 kg/m², 30 to <35 kg/m²,  $\geq$ 35 to < 40 kg/m²,  $\geq$ 40 kg/m²), baseline body weight (by quartiles), presence of comorbid conditions (none, hypertension, dyslipidemia, sleep apnea, CAD/CV disease), CV risk factors, presence of T2DM, tobacco use, albuminuria (normal: ACR

<30μg/mg; microalbuminuria: ACR 30 to 299 μg/mg; macroalbuminuria: ACR  $\ge$ 300 μg/mg), GFR (mL/min per 1.73 m² BSA); kidney damage with normal or increased GFR  $\ge$ 90; kidney damage with mildly decreased GFR 60 to 89; moderately decreased GFR 30 to 59; severely decreased GFR 15 to 29; kidney failure GFR <15 or dialysis; and type of diabetes medication used.

## 5.2.5 Medical History

The medical history verbatim descriptions (investigator terms from the Other Medical history and Current Medical Condition CRF) will be classified into standardized medical terminology using the Medical Dictionary for Regulatory Activities (MedDRA). Medical history will be coded to the MedDRA (Version 16.0 or higher) lower level term (LLT) closest to the verbatim term. The linked MedDRA preferred term (PT) and primary system organ class (SOC) will also be captured in the database. The number (percent) of subjects reporting a history of any medical condition will be summarized for each treatment group and overall.

In addition, separate summary tables by treatment group and overall will be provided for; Diabetes History, Cardiovascular History, Malignancy History, Psychiatric History, and Sleep Apnea/NAFLD History.

## 5.2.6 Prior and Concomitant Therapy

All investigator terms for medications recorded in the CRF will be coded to an 11-digit code using the World Health Organization Drug Dictionary (WHO DD). The number (percentage) of subjects who took prior and concomitant medications will be summarized on the Safety Analysis Set by treatment group, Anatomical Therapeutic Chemical (ATC) class, and WHO DD preferred term (PT). Prior medications will be defined as medications that stopped before the first dose of study drug.

Concomitant medications will be defined as any medications taken by the subject during the 30 days before first dose administration of study drug and continued the concomitant medication during the double blind phase or started a concomitant medication during the double blind phase. All medications will be presented in subject data listing.

## **5.2.7** Treatment Compliance

Overall compliance rate will be determined and defined as the difference in the tablets dispensed minus the number of tables returned, divided by the expected number of tablets to be taken, multiplied by 100. Subjects will be considered compliant while they are on BID or QD dosing. Descriptive statistics (n, mean, standard deviation, median minimum, maximum) and number (%) of subjects in compliance categories (<50%, 50 to <80%, 80 to  $\le120\%$ , >120%) will be provided for the entire double-blind phase. The Safety Analysis Set will be used. See Section 8.0 for derivation of compliance.

#### 5.3 DATA ANALYSIS GENERAL CONSIDERATIONS

## **5.3.1** Pooling of Centers

This study is a multicenter, international study with 476 sites. It is expected that due to the number of sites in this trial, sites will be pooled into regions, in order to have sufficient number of subjects per treatment group and CV disease strata. The countries participating in this study are Australia, Bahamas, Canada, Chile, Mexico, New Zealand, Poland, and the USA. The countries will be pooled into regions North America (USA, and Canada), and Rest of the World (Bahamas, Chile, Mexico, Poland, Australia and New Zealand). Region will be included as a covariate to explore region effects.

#### **5.3.2** Assessment of Effect Modification

In addition, to the primary and secondary analyses, outline in Sections 5.4.1 and 5.4.2 further exploratory analyses will be performed to assess for effect modification by a number of demographic and baseline variables outlined in Section 5.3.4 including:

- Age treated as continuous and as categorical
- Gender
- Presence of T2DM
- Race
- Ethnicity
- Region
- BMI as continuous and categorical
- eGFR as continuous and categorical

A separate analysis will be performed for each covariate.

## **5.3.3** Multiple Comparisons/Multiplicity

This study has two primary endpoints; MACE and MACE+. The following closed sequential gatekeeping testing procedure (SGTP) will be used to control the family-wise error rate (FWER) at  $\alpha = 0.05$  (two-sided) in testing the two primary endpoints (MACE and MACE+) and one key secondary endpoint, conversion to T2DM (revised per Amendment 02).

Let  $H_{01}$  be the gatekeeping null hypothesis for non-inferiority testing of the MACE endpoint using a non-inferiority margin of 1.4 for the hazard ratio.

Let  $H_{02}$ , and  $H_{03}$  be the null hypotheses for superiority testing: MACE+ and conversion to T2DM, respectively.

The SGTP testing hierarchy is presented below.

STEP1: At the interim analysis, test the non-inferiority hypothesis for MACE,  $H_{01}$  ( $\alpha = 0.025$ , one-sided). If  $H_{01}$  is rejected, then proceed to STEP2, otherwise stop testing and the trial will be stopped. This step will be performed as an interim analysis, see Section 6 for further details

• STEP2: At study completion, the hypothesis  $H_{02}$  ( $\alpha = 0.05$ , two-sided) is tested first. If the hypothesis is rejected then proceed to test  $H_{03}$  ( $\alpha = 0.05$ , 2-sided). If  $H_{02}$  is not rejected then testing stops at this point..

Figure 2 presents the SGTP (revised per Amendment 02)

#### Test MACE non-inferiority (a=0.025 1-sided) Step 1 Performed at STOR Interim Analysis Yes Step 2 Performed at MACE+ Study Completion superiority (a=0.05 2-sided) Significant? STOR Testing Conversion T2DM superiority (a=0.05 2-sided)

#### Flowchart for the Sequential Gatekeeping Testing Procedure

Figure 2 Flowchart for SGTP

MACE = major adverse cardiovascular events, MACE+ = MACE or hospitalization for unstable angina or heart failure, or any coronary revascularization; Step 1 will be performed when 460 adjudicated MACE events occurred, at the Interim Analysis. Step 2 will be performed upon Sponsor Notification of Study Completion which will occur once 1401 MACE+ events, and 2.5 years median treatment duration.

Analysis of other secondary endpoints will be used to support the results of primary analyses, thus no multiplicity adjustment will be performed.

#### 5.3.4 Examination of Subgroups

The primary endpoints will be analyzed for each of the demographic and baseline characteristics subgroups listed in Tables 2, and Baseline Cardiovascular Risk Level and Risk Factors, listed in Table 3. For categorical parameters, categories with sparse number of subjects will be collapse. The final set of categories will be determined prior to database lock.

Table 2 Subgroups of Demographic and Baseline Characteristics

Characteristic	Categories	
Age	≤65, ≥65 to < 75, ≥75 years	
Gender	Female, Male	
Race	White Black or African American Other Asian American Indian or Alaska Native Native Hawaiian or Other Pacific Islander Other	
BMI	$< 30 \text{ kg/m}^2$ $\ge 30 \text{ to} < 35 \text{ kg/m}^2$ $\ge 35 \text{ to} < 40 \text{ kg/m}^2$ $\ge 40 \text{ kg/m}^2$	
Waist circumference	Women <35 Inches (88cm) ≥35 Inches (88cm) Men <40 Inches (102cm) ≥40 Inches (102cm)	
Weight	$\leq 1^{st}$ Quartile >1 st Quartile to $\leq 2^{nd}$ Quartile >2 nd Quartile to $\leq 3^{rd}$ Quartile > 3 rd Quartile	
Duration of Type 2 Diabetes (years)	< 5 years     ≥ 5 to < 10 years     ≥ 10 to < 20 years     ≥ 20 years	
HbA1C	Non-diabetics (see Section 8)  Normal ( $< 5.7\%$ )  Pre-diabetes ( $\ge 5.7\%$ to $< 6.5\%$ )  Diabetics (see Section 8) $< 6.5\%$ $\ge 6.5\%$ to $< 7\%$ $\ge 7$ to $< 8\%$ $\ge 8$ to $< 9\%$ $\ge 9\%$	

Table 2 Subgroups of Demographic and Baseline Characteristics

Characteristic	Categories
FPG	<pre>< 100 mg/dL ≥ 100 to < 126 mg/dL ≥ 126 to < 150 mg/dL [≥ 7.0 mmol/L to < 8.3 mmol/L] ≥ 150 to < 220 mg/dL [≥ 8.3 mmol/L to < 12.2 mmol/L] ≥ 220 to < 300 mg/dL [≥ 12.2 mmol/L to < 16.7 mmol/L] ≥ 300 mg/dL [≥ 16.7 mmol/L]</pre>
Blood Pressure	Systolic BP (mmHg) <140 ≥140 Diastolic BP (mmHg) <90 ≥90
Renal Function (eGFR)	> 60 mL/min ≥ 30 to ≤ 60 mL/min < 30 mL/min
Albumin/creatinine ratio	<pre>< 30 mg/g [< 3.4mg/mmol]</pre>
Region and Country	North America (US/Canada) Rest of World (ROW) Europe Central and South America Australia/NZ
Baseline Diabetic Medication use	No medications/any insulin/oral meds without insulin GLP1 agonist/no GLP1 agonist SGLT2 inhibitor/no SGLT2 inhibitor SFU/no SF Metformin/no metformin SFU and Metformin/others Insulin/no insulin Insulin and SFU/others

Table 2 Subgroups of Demographic and Dasenic Characteristic	Table 2	Subgroups of Demographic and Baseline Characteristics
---	---------	---

Characteristic	Categories
	ASA
	Dual antiplatelet (ASA and P2Y12 receptor antagonist)
Baseline Cardiovascular Medication Use	Lipid Lowering Therapy
	Beta blocker
	ACEi/ARB/Aldosterone antagonist

Table 3 Subgroups of Baseline Cardiovascular Risk Level and Risk Factors

Characteristic	Categories
GVP: 14	Primary prevention - Patients with multiple risk factors for CV events, but without established CV disease
CV Risk Level	Secondary prevention - Patients with established CV disease
	By risk factor:
	- Dyslipidemia
	- Hypertension
Duignoga Proventier	- Renal impairment with either Calculated creatinine clearance ≥30 to ≤60 mL/min per the Chronic Kidney Disease Epidemiology Collaboration (CKD-EPI) equation or ACR≥30 μg/mg in spot urine
Primary Prevention (Risk Factors as defined in	- hsCRP > 3 mg/L
protocol inclusion criteria)	By number of risk factors in addition to T2DM:
•	1 additional risk factor (Dyslipidemia, hypertension, renal dysfunction or elevated hsCRP)
	2 additional risk factors
	3 additional risk factors
	4 additional risk factors
	Coronary artery disease
Secondary Prevention (Established	Peripheral vascular disease
CV Disease as defined in the protocol inclusion)	Cerebrovascular disease
r	Risk Scores(0,1-2, and 3 or greater) See Section 8 for definition

## 5.3.5 Handling of Missing Data, Drop-outs, and Outliers

Data will be monitored during the trial in order to minimize missing data. A detail retention plan in order to prevent missing data is found in Appendix 13.1. The primary endpoints are time to event endpoints for MACE/MACE+. Every effort will be made to find subjects who are lost to follow-up using patient finder services. Once these subjects are found the sites will contact the

subject and will try to obtained vital status information on the subject. Primary consideration is to establish if the subject is dead or alive.

## **5.3.6** Other Considerations

Potential MACE/MACE+ events will be recorded throughout the study. During this study, the endpoints of MACE and MACE+ will need to be reported in an expedited fashion by investigators to the Clinical Endpoint Committee (CEC) and to the Eisai Product Safety Department. MACE/MACE+ events will be recorded on the Adverse Event (AE) case report form, but these events will not be considered as AEs, nor will they be recorded as serious adverse events (SAEs) in the clinical trial safety database or be required to be reported to regulatory authorities in an expedited timeframe, with the exception of MACE or MACE+ events that are considered by the investigator to be at least possibly related to the study drug (i.e., where there is evidence to suggest a causal relationship).

Details of which events to report, how to report, and the required supporting documentation will be detailed in a separate manual provided to the sites.

#### Adjudication of Component Events for MACE/MACE+

The component events of MACE; MI, or stroke, or CV death and the component events of MACE+; MI, or stroke, or CV death, or hospitalization for unstable angina or HF, or any coronary revascularization, will be adjudicated by the CEC, in order to reduce intra- and intersite variability. The CEC will centrally review each potential component event of MACE and MACE+ to ensure standardization of data collection and interpretation of such events reported throughout the study. The CEC will determine whether each potential component event meets criteria for MACE or MACE+. The CEC will remain blinded to treatment allocation and its activities and the criteria for classification of each component event of MACE/MACE+ will be documented in the CEC Charter, see Appendix 13.1.1.

## Adjudication of Conversion to Diabetes Events

The conversion to diabetes events will be adjudicated by the CEC Diabetes Adjudication Charter, in order to reduce intra- and inter-site variability. The CEC will centrally review each potential event to ensure standardization of data collection and interpretation of such events reported throughout the study. The CEC will determine whether each potential event meets criteria for conversion to diabetes. The CEC will remain blinded to treatment allocation and its activities and the criteria for classification of each event will be documented in the charter, see Appendix 13.1.4.

#### 5.4 EFFICACY ANALYSES

The primary and key secondary endpoints, MACE, MACE+, and conversion to T2DM, will be analyzed using a Cox proportional hazards model that includes factors for treatment and stratification variable (presence of established CV disease or CV risk factors without established CV disease). For other secondary and exploratory endpoints a two-sided  $\alpha = 0.05$  significance level will be used. The primary safety analysis for MACE will be conducted when 460

adjudicated MACE events have been recorded at the interim analysis; the other analyses will be conducted when 1401 adjudicated MACE+ events have been recorded, and the study has completed. See Section 6 for Interim Analysis Plan.

Secondary and exploratory time-to-event endpoints will be analyzed using a Cox proportional hazards model that includes factors for treatment and stratification variable (presence of established CV disease or CV risk factors without established CV disease), except for those endpoints that used the population with no T2DM at Baseline, the CV stratification variable will not be included in the model.

For all time-to-event endpoints, plots of the Kaplan-Meier estimate of the survival function, cumulative hazard function, kernel-smoothed estimate of the hazard function, and median time estimates along with  $100(1-\alpha)$  % CI will be presented. In addition, parameter estimates, standard errors, hazard ratio and  $100(1-\alpha)$  % CI will presented. In addition, event rates will be presented per 100 patient years where appropriate.

Details of the censoring algorithms for time-to-event endpoints are presented in Section 8.5.

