## 3.3 OVERALL STUDY DESIGN AND PLAN

This will be a multicenter, randomized, double-blind, placebo-controlled, parallel-group study in overweight and obese subjects with CV disease and/or multiple CV risk factors. Approximately 12,000 subjects will be randomized to 2 treatment groups in a ratio of 1:1, stratified by the presence of established CV disease (~80%) or CV risk factors without established CV disease

(~20%). The 80% of subjects in the established CV disease strata will consist of a group with T2DM (approximately 30% of the total number of subjects in the study) and a group without T2DM (approximately 50% of the total number of subjects in the study). The 20% of subjects in the strata with CV risk factors but without established CV disease will all have T2DM, as well as additional risk factors. Therefore, approximately 50% of the total number of subjects in the study will have T2DM (Table 1).

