## 5.4.2 Key Secondary Analysis (revised per Amendment 02)

• Time to conversion to T2DM (Superiority). The estimate of the hazard ratio of lorcaserin HCl to placebo and the corresponding two-sided 95% CI will be calculated. The Prediabetes and Total Time Analyses Sets will be used as the primary analysis. The Prediabetes along with the On-Treatment Analysis Set and the On-Treatment plus 30 Days Analysis Set will be used as a sensitivity analysis at Study Completion (revised per Amendment 02).

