## 5.4.3 Secondary Endpoint Analyses

For the following endpoints, a Cox proportional hazards model with factors for treatment and stratification variable (presence of established CV disease or CV risk factors without established CV disease) will be used. The estimate of the hazard ratio of lorcaserin HCl to placebo and the corresponding 2-sided 95% CI will be calculated. See Section 8.5 for details on censoring algorithms for the time-to-event endpoints.

The secondary endpoints are considered as supportive analysis to the primary endpoints and key secondary endpoint, therefore no correction for Type I error rate will be performed.

- The time-to-event of each component of MACE+. The Total Time Analysis Set will be used as the primary analysis. The On-Treatment Analysis Set and the On-Treatment plus 30 Days Analysis Set will be used as sensitivity analyses.
- Time-to-event of all-cause mortality. The Total Time Analysis Set will be used as the primary analysis. The On-Treatment Analysis Set and the On-Treatment plus 30 Days Analysis Set will be used as sensitivity analyses.
- Time-to-event of new onset renal impairment or worsening existing renal impairment in all subjects. The ITT Analysis Set will be used for this analysis. (revised per Amendment 02)
- Time-to-event of new onset renal impairment or worsening existing renal impairment in subjects with T2DM at Baseline. The T2DM Analysis Set will be used for this analysis.
- Time-to-event of new onset renal impairment or worsening existing renal impairment in subjects with prediabetes at Baseline. The Prediabetes Analysis Set will be used for this analysis. (revised per Amendment 01)
- Time-to-event of improvement in renal function. The T2DM Analysis Set will be used for this analysis.
- Time-to conversion to T2DM in subjects without any type of diabetes at Baseline.
   The Nondiabetes Analysis Set will be used for this analysis. (revised per Amendment 01)
- o Time to conversion to normal glucose homeostasis (HbA1c ≤5.6% and fasting plasma glucose <100 mg/dL without any antidiabetic treatment). The Prediabetes Analysis Set will be used for this analysis. (revised per Amendments 01 and 02)

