    - o random plasma glucose > or = 200 with associated symptoms of hyperglycemia prior to or at Baseline
- Subject who are Pre-diabetic at Baseline: Subject must meet all the following conditions;
  - o On the Diabetes History Form "Clinical diagnosis of diabetes?" = "No" and
  - o Not initiated any diabetes treatment prior to or at Baseline and
  - At least one of the following:
    - o HbA1c 5.7% to <6.5% or
    - FPG 100 to 125 mg/dL (5.55 to 6.94 mmol/L) between Screen and Baseline and
  - None of the following where available
    - o HbA1c  $\geq$  6.5% in all central or local labs assessments prior to or at Baseline and
    - o FPG ≥ 126 mg/dL (7.0 mmol/L) in all central or local labs assessments prior to or at Baseline and
    - o random plasma glucose > or = 200 with associated symptom of hyperglycemia prior to or at Baseline and
    - o 2-hour plasma glucose ≥ 200 mg/dL(11.1mmol/L) by an OGTT test prior to or at Baseline and
- Subject who are Normoglycemic at Baseline: Subject must meet the following conditions:
  - o On the Diabetes History Form "Clinical diagnosis of diabetes?" = "No" AND
  - o Not initiated any diabetes treatment prior to or at Baseline AND
  - o None of the following where available:
    - o HbA1c  $\geq$  5.7% in all central or local labs assessments prior to or at Baseline

- o FPG ≥ 100 mg/dL (5.55 mmol/L) in all central or local labs assessments prior to or at Baseline
- 2-hour plasma glucose ≥ 200 mg/dL(11.1mmol/L) by an OGTT test prior to or at Baseline
- Random glucose > or = 200 with associated symptoms of hyperglycemia prior to or at Baseline
- Subject is not otherwise defined as 'pre-diabetic' at baseline
- Subjects who are T2DM at Baseline: Subject must meet at least one of the following conditions.
  - o On the Diabetes History Form "Clinical diagnosis of diabetes?" = "Yes" and Type of Diabetes = 2 on Diabetic History CRF or
  - o HbA1c  $\geq$  6.5% prior to or at Baseline in either central or local labs or
  - o FPG ≥ 126 mg/dL (7.0 mmol/L) prior to or at Baseline in either central or local labs or
  - o 2-hour plasma glucose  $\geq 200 \text{ mg/dL}(11.1 \text{mmol/L})$  by an OGTT test or
  - Random plasma glucose > or = 200 with associated symptoms of hyperglycemia prior to or at Baseline
  - o Any diabetes treatment prior to or at Baseline
- Subjects who are T1DM at Baseline: Subject must meet the following conditions.

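### The key secondary Cox model for conversion to T2DM has no informative covariate; prespecifying baseline HbA1c and FPG would gain power without new data

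*SAP*

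**What the plan says.** SAP 5.4 covers MACE, MACE+ and the key secondary endpoint in one sentence: "conversion to T2DM, will be analyzed using a Cox proportional hazards model that includes factors for treatment and stratification variable". SAP 5.4.2 fixes the population for conversion ("The Prediabetes and Total Time Analyses Sets will be used as the primary analysis") and adds no covariate. Protocol 9.7.1.6 names the stratum only for MACE and MACE+; its conversion paragraph lists no covariates.

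The next paragraph of SAP 5.4 gives secondary and exploratory time-to-event endpoints the same model, "except for those endpoints that used the population with no T2DM at Baseline, the CV stratification variable will not be included in the model". SAP 5.4.3 then restores the stratum for a list that includes conversion to T2DM in the Nondiabetes set and conversion to normal glucose homeostasis in the Prediabetes set. Protocol 9.7.1.7 does the same.

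On the stratum, SAP 3.3 says: "The 20% of subjects in the strata with CV risk factors but without established CV disease will all have T2DM". SAP Table 1 shows 0% without T2DM in that column.

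The SAP section 8 definitions require, for prediabetes, at least one of "HbA1c 5.7% to <6.5% or" and "FPG 100 to 125 mg/dL (5.55 to 6.94 mmol/L) between Screen and Baseline", with no diabetic-range value. HbA1c and FPG are both scheduled at Screening and Visit 2 for all subjects (Protocol 9.5.1.3 and Table 4).

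**The concern.** A covariate that takes one value in the analysed population has no estimable coefficient. The key secondary model therefore reads as adjusted but in practice contains treatment alone.

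The event is reached mainly by crossing HbA1c 6.5% or FPG 126 mg/dL, from a population defined by lying just below those limits. The starting values are the natural predictors. The SAP already adjusts for baseline HbA1c in its 6-month ANCOVAs (5.4.3 and 5.8), but in no conversion analysis. The HbA1c and FPG subgroups in 5.3.4 cover the primary endpoints only, and the effect-modification list in 5.3.2 contains neither measure.

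At stake is efficiency on the only secondary endpoint under alpha control (SAP 5.3.3). Amendment 02 moved it out of the primary position because conversions were slow to accrue. SAP section 8 triggers study completion by MACE+ events and treatment duration, although SAP section 6 still mentions conversion events, so 457 conversions are not assured.

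**Working it through.** **1. Is the stratum informative?** Prediabetic subjects have no diabetes diagnosis, treatment or diabetic-range value (SAP section 8). Subjects in the risk-factor stratum all have T2DM (SAP 3.3, Table 1). Apart from stratification errors, the two groups do not overlap, so the stratum is constant. A trial Cox fit with a constant column returned no estimate.

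**2. The plan's own figure.** Inputs from SAP section 4: D = 457 events, HR 0.75, two-sided alpha 0.05, placebo rate 4% a year, drop-out 5% a year, 15-month accrual, 54 months in total. N = 33% of 12,000 = 3,960, or 1,980 per arm.

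- Schoenfeld: z = ½ × √457 × |ln 0.75| − 1.96 = ½ × 21.378 × 0.2877 − 1.96 = 1.115; power 86.8%.
- Freedman: z = √457 × (0.25/1.75) − 1.96 = 1.094; power 86.3%.
- Events per arm, with event rate λ and drop-out rate δ: n × λ/(λ+δ) × {1 − [e^(−3.25(λ+δ)) − e^(−4.5(λ+δ))]/[1.25(λ+δ)]}. Placebo: 1,980 × 0.4444 × 0.2941 = 258.8. Lorcaserin: 1,980 × 0.375 × 0.2662 = 197.7. Total 456, against 457 stated.

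The 86% is an ordinary unadjusted calculation, and it reproduces.

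**3. Adding the covariate, with 0.75 as the conditional hazard ratio.** The documents give no prognostic strength, so a range is assumed for one standardised baseline glycaemia variable. Two simulations used 3,960 subjects and the inputs above. Set A tuned the baseline hazard to about 457 events (3,500 trials per row, Monte Carlo error about 0.6 points). Set B cut each trial at the 457th event (2,000 trials per row, about 0.8 points).

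| Set | HR per SD (assumed) | Power, unadjusted | Power, adjusted | Gain (points) |
|---|---|---|---|---|
| A | 1.5 | 85.9% | 86.8% | 0.9 |
| B | 1.65 | 85.7% | 86.9% | 1.2 |
| A | 2.0 | 84.7% | 87.2% | 2.5 |
| B | 2.23 | 82.7% | 86.4% | 3.7 |
| A | 2.5 | 82.6% | 87.4% | 4.8 |
| B | 2.72 | 79.9% | 86.1% | 6.2 |
| A | 3.0 | 78.2% | 86.5% | 8.3 |
| B | 3.49 | 74.8% | 85.3% | 10.5 |

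In set B the mean unadjusted hazard ratio was 0.751, 0.760, 0.770 and 0.780 in turn, while the standard error of the log hazard ratio stayed near 0.094 in both models. The gain comes from the size of the estimate, not from its precision. With a covariate of no effect, set B gave 85.3% unadjusted and 85.2% adjusted, so nothing is lost.

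**4. With 0.75 as the unadjusted hazard ratio.** The squared ratio of adjusted to unadjusted log HR/SE in set B was 1.033, 1.110, 1.198 and 1.327. Scaling the planned ½√457 × |ln 0.75| = 3.075 by the square root of each, for example 3.075 × √1.198 − 1.96 = 1.406, gives power of 87.8%, 90.0%, 92.0% and 94.3%, against 86.8% unadjusted.

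**The case against.** A Cox model with treatment and the stratification factor is conventional, and leaving out a prognostic covariate does not inflate type I error. SAP section 4 states the 25% reduction without conditioning on anything, so the natural reading is an unadjusted hazard ratio. On that reading the planned model delivers the planned power and adjustment is a bonus. All of this stands.

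The gain rests on assumed strengths. Entry limits narrow the spread of HbA1c and FPG in this set, and nothing in the documents supports the upper end of the range. That stands too.

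The exception in SAP 5.4 may already remove the stratum for this endpoint. Its wording speaks of secondary endpoints, while SAP 5.4.3 separates the two classes: "The secondary endpoints are considered as supportive analysis to the primary endpoints and key secondary endpoint". The opening sentence of 5.4 names conversion explicitly. The text is ambiguous, but on either reading no informative covariate remains. A constant term does not alter the treatment estimate, so that part is a matter of wording.

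Conversion is also tested only if MACE+ superiority is shown, which limits the consequence.

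A reader might infer that the planned analysis is biased or underpowered. The documents do not support this. The drift of the hazard ratio towards 1 reflects a different, valid estimand, and a shortfall against 86% appears only if 0.75 is read as conditional.

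**Conclusion.** The point holds as an inexpensive improvement in efficiency. The key secondary model has no informative covariate, by design of the strata, and the two obvious predictors are unused although scheduled for everyone. The planned test is valid and its stated power reproduces.

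If 0.75 is conditional, adjustment adds about 1 point of power at an assumed 1.5-1.65 per SD, about 2.5 to 6 points at 2.0-2.7, and 8 to 10 points at 3.0-3.5. If 0.75 is unadjusted, power rises from about 87% to about 88-94%. Both results assume a single, correctly modelled baseline variable.

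Two further inferences would go too far. Scheduled does not mean always available: either measure alone qualifies a subject as prediabetic, so a baseline value may be missing. And the stratum is constant by design, but stratification errors could leave a few exceptions.

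Separately, SAP 5.4 and 5.4.3 conflict for the Nondiabetes and normal-glucose endpoints, and need reconciling whatever is decided on covariates.

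**What to change.** Before unblinding:

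- **Stratum.** Reconcile SAP 5.4, 5.4.2 and 5.4.3 so that the CV stratum is dropped for every conversion endpoint in subjects without T2DM: the key secondary, conversion in the Nondiabetes set, and conversion to normal glucose homeostasis. The prediabetes renal endpoint in 5.4.3 is caught by the same conflict. Align Protocol 9.7.1.7.
- **Covariates.** Prespecify baseline HbA1c and baseline FPG as continuous covariates in the conversion models, using the last value at or before randomization as in SAP section 8. State the functional form and a simple rule for a missing baseline value.
- **Estimand.** State that the adjusted hazard ratio is conditional on baseline glycaemia and can lie further from 1 than the unadjusted one. Report the unadjusted hazard ratio as supportive.
- **Protocol 9.7.1.6.** Add the covariates for conversion; no stratum is named there for this endpoint, so none has to be replaced.

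The cost is wording and a small programming change. No new data are needed.
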